datasets, depending on the number of imputed monotone datasets that are required. The seed may be changed after unblinding in case of any issues with the imputation process, and it will be documented in the CSR if any change is required.

3. For each completed dataset, compute the necessary derived variables. The dichotomous success rate (clear or almost clear with at least a 2-point change from baseline) will be derived. The results obtained will be analyzed using the Cochran-Mantel-Haenszel (CMH) analysis for each of the complete analysis data sets stratified by baseline S-IGA score category, baseline B-IGA score category, and country. The results will be combined into one multiple imputation inference (odds ratio, associated CI, and *P* value) using PROC MIANALYZE as illustrated⁴.

This approach to imputation should be superior to other strategies such as carrying forward the last available observation, which may yield unrealistic imputed values. Also, the use of multiple imputation avoids the problem of artificially increasing power through data imputation associated with single-imputation methods because it accounts for the uncertainty associated with the imputation. Other missing data will not be imputed, with the exception of incomplete dates as described in Section 6.1.8. For responder analyses, missing data will be treated as a nonresponse with the exception of S-IGA. Only observed data will be summarized using descriptive statistics.

The SAS pseudo code for the multiple imputation process is listed below:

Step 1:

```
proc mi data=example seed=34978264 nimpute=XX round=1 out=example_1;  
  mcmc impute=monotone;  
  var <baseline score> ..... <visit8 score>;  
run;
```

Step 2:

```
proc mi data=example_1 seed=51192215 nimpute=XX out=example_2;  
  class <treatment> <country>;  
  monotone regpmm(<baseline score> ..... <visit8 score>);  
  var <treatment> <country> <baseline score> ..... <visit8 score>;  
run;
```

XX will be determined based on the proportion of missing data across visits.

Step 3: This step involves running CMH test stratified by baseline S-IGA score category, baseline B-IGA score category, and country on each completed dataset and combining the results using PROC MIANALYZE.

```
proc freq data=example noprint;  
  by <imputationnumber> <visit> ;  
  tables <country> * <BL S-IGA cat> * <BL B-IGA cat> * <treatment> *  
    <outcome> / cmh alpha=0.05;  
  output out=example_stat cmh;  
run;
```

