6.2. Special Handling for COVID-19 Disruptions

In some cases, study visits will have to be delayed/not performed as a result of COVID-19 disruptions (e.g., sites were closed or subjects were under stay-at-home orders). Where possible, study sites may collect post-baseline data from subjects remotely by telephone, traditional mail, and/or email; this will be clearly documented in the source. If possible, sites should adhere to the protocol visit window for remote data collection.

Investigator assessments and subject questionnaires normally completed directly in the electronic patient reported outcomes (ePRO) tablet during on-site visits should be completed on the appropriate paper source documents. The following assessments/questionnaires are approved to be collected via telemedicine/remotely:

- WI-NRS/SI-NRS
- DLQI/CDLQI
- C-SSRS
- PHQ-8/PHQ-A
- Subject Local Tolerability
- PSD

The following assessments cannot be completed via telemedicine/remotely:

- S-IGA/B-IGA
- BSA
- Investigator Local Tolerability
- PASI/mPASI
- PSSI
- Subject Weight

Study visits and procedures must be followed per protocol whenever possible. Any specific changes in study conduct that deviate from the protocol should be communicated to the institutional review board and Sponsor. All protocol deviations which occurred as a result of COVID-19 disruptions (e.g., visits out of window, missed assessments, etc.) will be differentiated from other protocol deviations.

Subjects who were affected by COVID-19 disruptions by either missing their Week 8 visit or being discontinued before having a Week 8 visit due to COVID-19 related disruptions will be excluded from the mITT population, as described in Section 5.

7. Study Subjects and Demographics

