Sensitivity analyses of the primary endpoint will also be performed using the original (nonimputed) dataset. These will include a repeated measures logistic regression model (GEE) with S-IGA success as the dependent variable and treatment, country, visit, and baseline S-IGA score as the independent variables.

Achievement of a score of clear will also be analyzed using the CMH test, on nonimputed data.

A tipping point analysis will be performed as described in Section 6.1.4.2. For the tipping point analysis, a figure will be provided that displays the P values in the analysis plotted against the range of shift parameters; included in this figure will be the shift parameters and P values for the range of shift parameters to provide information on where the analysis tips from significant to non-significant.

Subgroup Analyses – Observed Data

For the primary endpoint of IGA success (S-IGA of “Clear” or “Almost Clear” plus a 2-grade improvement from baseline at Week 8), the CMH analysis will be performed on the following subgroups, using observed data:

- Topical Corticosteroids – Naïve Subjects
- Topical Vitamin D Derivatives – Naïve Subjects
- Psoriasis involvement on the knee and/or elbow
- Subjects who achieved both S-IGA and B-IGA success at Week 8
- By Study Site

Subgroup Analyses – Multiple Imputation Data

For the primary endpoint of IGA success (S-IGA of “Clear” or “Almost Clear” plus a 2-grade improvement from baseline at Week 8), the CMH analysis will be performed on the following subgroups, using multiple imputation data:

- Baseline S-IGA = 3
- Baseline S-IGA = 4
- Age Category = 12-17 years
- Age Category = ≥ 18 years
- Subjects who achieved both S-IGA and B-IGA success at Week 8

Continuous Data Analysis

Analysis of change from baseline in S-IGA scores at Weeks 2, 4, 8, and 9 will be performed using descriptive summaries (mean, median, inter-quartile range) by treatment group and study visit. These descriptive statistics will also be presented based on the multiple imputation data.

All Analyses

All other missing data for all other analyses and summaries will remain missing and will not be imputed. All weeks will be included in these analyses, although only Week 8 using the ITT population will be included in the testing strategy.

The primary efficacy analysis will be based on ITT population, and all of the above analyses will be repeated for the mITT population.

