 - Subjects with psoriasis involvement on the knee and/or elbow
 - Subjects who achieved S-IGA and B-IGA success at Week 8
 - By study site
- Analysis of S-IGA score of clear (included in the fixed-sequence testing strategy)
- Analysis of S-IGA success based on the following subgroups (both ITT and mITT

populations, multiple imputation data only):

- Baseline S-IGA = 3
- Baseline S-IGA = 4
- Age Category: 12-17 years
- Age Category: ≥ 18 years
- Subjects who achieved S-IGA and B-IGA success at Week 8
- Achievement of success in PSSI-100
- Time to achievement of PSSI-75 and PSSI-90
- Achievement of success in mPASI-50, mPASI-75, and mPASI-90

Additional safety analyses have been added in the SAP which are not specified in the protocol, as requested by the Sponsor. They are:

- Incidence of TEAEs leading to study discontinuation by SOC and preferred term
- Incidence of related TEAEs by preferred term
- Summarization of weight loss categories by intentionality of weight loss
- Shift tables for BMI categories

11. Other Planned Analysis

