Odds Ratio (95% CI) [3]	X.XX (X.XX, X.XX)	
P value [3]	X.XXXXX	

Repeat for all Week 4, Week 8, and Week 9.

Abbreviations: B-IGA = body investigator global assessment; CI = confidence interval; S-IGA = scalp investigator global assessment.
Note: Percentages are n/Number of subjects in the ITT population within planned treatment at each visit*100. Baseline is the last non-missing measurement taken before the first application of study drug.
[1] S-IGA Success ("Yes") is defined as an S-IGA score of "Clear" or "Almost Clear" plus a ≥2-grade improvement from baseline; "No" otherwise.
[2] 95% CIs for "Yes" are obtained using Wilson method.
[3] The odds ratio, 95% CI, and P value are obtained from Cochran Mantel Haenszel test (stratified by country, baseline S-IGA category, and baseline B-IGA category) comparing roflumilast foam 0.3% to vehicle. Reference Listings: 16.2.6.1, 16.2.6.2

Table 14.2.1.5.2

Summary of Scalp Investigator Global Assessment (S-IGA) Grades and Success by Study Visit – Observed Data
Categorical Results

ITT Population - Topical Corticosteroids - Naïve Subjects

(Same shell as Table 14.2.1.5.1; add 16.2.4.2 to reference listings; change “Percentages” footnote to be “Percentages are n/Number of subjects in the ITT population that are topical corticosteroids – naïve subjects within planned treatment at each visit*100.”)

Table 14.2.1.5.3

Summary of Scalp Investigator Global Assessment (S-IGA) Grades and Success by Study Visit – Observed Data
Categorical Results

ITT Population - Topical Vitamin D Derivative - Naïve Subjects

(Same shell as Table 14.2.1.5.1; add 16.2.4.2 to reference listings; change “Percentages” footnote to be “Percentages are n/Number of subjects in the ITT population that are topical vitamin D derivative – naïve subjects within planned treatment at each visit*100.”)

Table 14.2.1.5.4

Summary of Scalp Investigator Global Assessment (S-IGA) Grades and Success by Study Visit – Observed Data
Categorical Results

ITT Population - Subjects with Psoriasis Involvement on the Knee and/or Elbow

(Same shell as Table 14.2.1.5.1; add 16.2.4.2 to reference listings; change “Percentages” footnote to be “Percentages are n/Number of subjects in the ITT population that have psoriasis involvement on the knee and/or elbow within planned treatment at each visit*100.”)

Table 14.2.1.5.5

Summary of Scalp Investigator Global Assessment (S-IGA) Grades and Success by Study Visit – Observed Data
Categorical Results

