ITT Population - Subjects who Achieved S-IGA and B-IGA Success at Week 8

(Same shell as Table 14.2.1.5.1; change “Percentages” footnote to be “Percentages are n/Number of subjects in the ITT population that achieved both S-IGA and B-IGA success at Week 8 within planned treatment at each visit*100.”)

Table 14.2.1.5.6
 Summary of Scalp Investigator Global Assessment (S-IGA) Grades and Success by Study Visit – Observed Data
 Categorical Results
 ITT Population – by Study Site

Study Site: S-ITENAM (Site SITEID)	Roflumilast Foam 0.3% (N=XX)	Vehicle (N=XX)
Study Visit Category/Statistic		
Baseline	XX	XX
0 = Clear	XX (XX.X%)	XX (XX.X%)
1 = Almost Clear	XX (XX.X%)	XX (XX.X%)
2 = Mild	XX (XX.X%)	XX (XX.X%)
3 = Moderate	XX (XX.X%)	XX (XX.X%)
4 = Severe	XX (XX.X%)	XX (XX.X%)
Week 2	XX	XX
0 = Clear	XX (XX.X%)	XX (XX.X%)
1 = Almost Clear	XX (XX.X%)	XX (XX.X%)
2 = Mild	XX (XX.X%)	XX (XX.X%)
3 = Moderate	XX (XX.X%)	XX (XX.X%)
4 = Severe	XX (XX.X%)	XX (XX.X%)
S-IGA Success [1]		
Yes	XX (XX.X%)	XX (XX.X%)
95% CI [2]	(X.XX, X.XX)	(X.XX, X.XX)
No	XX (XX.X%)	XX (XX.X%)
Odds Ratio (95% CI) [3]	X.XX (X.XX, X.XX)	
P value [3]	X.XXXXX	

Repeat for all Week 4, Week 8, and Week 9.

Abbreviations: B-IGA = body investigator global assessment; CI = confidence interval; S-IGA = scalp investigator global assessment.
 Note: Percentages are n/Number of subjects in the ITT population within planned treatment and study site at each visit*100. Baseline is the last non-missing measurement taken before the first application of study drug.
 [1] S-IGA Success (“Yes”) is defined as an S-IGA score of “Clear” or “Almost Clear” plus a ≥2-grade improvement from baseline; “No” otherwise.
 [2] 95% CIs for “Yes” are obtained using Wilson method.
 [3] The odds ratio, 95% CI, and P value are obtained from Cochran Mantel Haenszel test (stratified by country, baseline S-IGA category, and baseline B-IGA category) comparing roflumilast foam 0.3% to vehicle.
 Reference Listings: 16.2.6.1, 16.2.6.2

Programming note: sort by ADSL.SITEID. Format study site as shown (e.g., “Study Site Name (Site 01)”).

Table 14.2.1.6.1

Summary of Scalp Investigator Global Assessment (S-IGA) Grades and Success by Study Visit – Observed Data
Categorical Results
mITT Population

(Same shell as Table 14.2.1.5)

Table 14.2.1.6.2

Summary of Scalp Investigator Global Assessment (S-IGA) Grades and Success by Study Visit – Observed Data
Categorical Results
mITT Population - Topical Corticosteroids - Naïve Subjects

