(Same shell as Table 14.2.1.5.2; add 16.2.4.2 to reference listings; change “Percentages” footnote to be “Percentages are n/Number of subjects in the mITT population that are topical corticosteroids – naïve subjects within planned treatment at each visit*100.”)

Table 14.2.1.6.3

Summary of Scalp Investigator Global Assessment (S-IGA) Grades and Success by Study Visit – Observed Data
Categorical Results
mITT Population - Topical Vitamin D Derivative - Naïve Subjects

(Same shell as Table 14.2.1.5.3; add 16.2.4.2 to reference listings; change “Percentages” footnote to be “Percentages are n/Number of subjects in the mITT population that are topical vitamin D derivative – naïve subjects within planned treatment at each visit*100.”)

Table 14.2.1.6.4

Summary of Scalp Investigator Global Assessment (S-IGA) Grades and Success by Study Visit – Observed Data
Categorical Results
mITT Population - Subjects with Psoriasis Involvement on the Knee and/or Elbow

(Same shell as Table 14.2.1.5.4; add 16.2.4.2 to reference listings; change “Percentages” footnote to be “Percentages are n/Number of subjects in the mITT that have psoriasis involvement on the knee and/or elbow within planned treatment at each visit*100.”)

Table 14.2.1.6.5

Summary of Scalp Investigator Global Assessment (S-IGA) Grades and Success by Study Visit – Observed Data
Categorical Results

mITT Population - Subjects who Achieved S-IGA and B-IGA Success at Week 8

(Same shell as Table 14.2.1.5.1; change “Percentages” footnote to be “Percentages are n/Number of subjects in the mITT population that achieved both S-IGA and B-IGA success at Week 8 within planned treatment at each visit*100.”)

Table 14.2.1.6.6

Summary of Scalp Investigator Global Assessment (S-IGA) Grades and Success by Study Visit – Observed Data
Categorical Results

mITT Population – by Study Site

(Same shell as Table 14.2.1.5.6;)

Table 14.2.1.7.1

Summary of Scalp Investigator Global Assessment (S-IGA) Grades and Success by Study Visit – Multiple Imputation
Categorical Results
ITT Population

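### A CMH subgroup defined by Week 8 S-IGA success has no Week 8 test to report, and the GEE term list should name the treatment-by-visit effect that its table implies

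*SAP*

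**What the plan says.** **Achiever subgroup.** SAP Section 8.1.1 has two lists of subgroups in which the CMH analysis of Week 8 S-IGA success is to be run, one on observed data and one on multiply imputed data. Both include "Subjects who achieved both S-IGA and B-IGA success at Week 8". Section 10 repeats the item in both of its lists of sponsor-requested additions ("Subjects who achieved S-IGA and B-IGA success at Week 8"), for the ITT and mITT populations.

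The shells in Section 14.2 leave no doubt about the denominator. Tables 14.2.1.5.5 and 14.2.1.7.6 take percentages over the "Number of subjects in the ITT population that achieved both S-IGA and B-IGA success at Week 8 within planned treatment at each visit". Tables 14.2.1.6.5 and 14.2.1.8.6 use the "Number of subjects in the mITT population that achieved both S-IGA and B-IGA success at Week 8 within planned treatment at each visit". All four inherit the layout of Table 14.2.1.5.1, the imputed pair through Table 14.2.1.7.1. Its footnote 3 reads "The odds ratio, 95% CI, and P value are obtained from Cochran Mantel Haenszel test", and its rows repeat at Weeks 2, 4, 8 and 9.

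**GEE.** Section 8.1.1 and footnote 3 of Table 14.2.1.9 give the same independent variables: treatment, country, visit and baseline S-IGA score. Neither mentions a treatment-by-visit term. The shell, shared by Table 14.2.1.10, has a separate row with odds ratio and CI for each of Weeks 2, 4, 8 and 9. Footnote 3 specifies an unstructured correlation, then Toeplitz, compound symmetry and AR(1) if the fit does not converge.

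**The concern.** The other CMH subgroups in Section 8.1.1 are, site aside, defined by baseline disease, treatment history or age. This one is defined by the endpoint itself, so it cannot support a test of that endpoint. At the remaining visits the arms are compared after selection on a post-randomisation result, so the comparison is no longer protected by randomisation. Its P values would nevertheless appear in the same format as those of the genuine subgroups.

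The GEE is described as a sensitivity analysis of the primary endpoint, whose estimand in Section 8.1.1 is the odds ratio at Week 8. If the model is programmed exactly as listed, the Week 8 row would show an average over visits. That average includes Week 9, which Section 3.1 places one week after the last dose. What to print for an undefined statistic, and whether to add an interaction, would then be settled by a programmer, possibly after unblinding.

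**Working it through.** The plan states no figure on this point, so there is none to reproduce.

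**(a) CMH among achievers.** In stratum h let a, b be active successes and failures, c, d vehicle successes and failures, and n = a + b + c + d.

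- CMH numerator: sum of [a − (a+b)(a+c)/n]
- CMH variance: sum of [(a+b)(c+d)(a+c)(b+d) / (n²(n−1))]
- Mantel-Haenszel odds ratio: sum(ad/n) / sum(bc/n)

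At Week 8 every member is a success, so b = d = 0 in every stratum. The numerator term becomes a − a(a+c)/(a+c) = 0. The variance carries the factor b + d = 0. The odds ratio is 0/0. With illustrative strata (20,0,3,0), (15,0,2,0) and (10,0,1,0), all four sums came out as 0. Standard software returned a missing value for both the odds ratio and the test. The result does not depend on the counts.

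Extent: 4 tables × 4 visits = 16 sets of odds ratio, CI and P value. Of these, 4 × 1 = 4 do not exist, and 4 × 3 = 12 compare responders selected after randomisation.

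Likely size of the subset: the inputs are the 200 and 100 subjects and the 32.2% and 9.8% planning rates in SAP Section 3.2. The documents give no B-IGA rate and no overlap with S-IGA, so I assume that B-IGA success has the same planning rates.

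| Assumed overlap | Active | Vehicle |
|---|---|---|
| Complete | 200 × 0.322 = 64.4 | 100 × 0.098 = 9.8 |
| Independent | 200 × 0.322² = 20.7 | 100 × 0.098² = 0.96 |

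Under independence, the chance that no vehicle subject enters the subset is (1 − 0.098²)^100 = 0.38. Independence is an extreme case for two scores on the same treated patient, and the undefined Week 8 test does not rest on it.

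**(b) GEE.** With main effects only, logit P = intercept + βT·treatment + country + visit + baseline. Subtracting vehicle from active at any visit leaves βT, so all four rows show exp(βT). Adding treatment-by-visit gives βT + γ(visit), which can differ by row.

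As an illustration, I used one artificial dataset of 200 against 100 subjects. Assumed success rates (active/vehicle) were 8/6%, 20/8% and 30/10% at Weeks 2, 4 and 9, with the planning rates 32.2/9.8% at Week 8. The listed model gave a single odds ratio of 3.37. With the interaction, the values at Weeks 2, 4, 8 and 9 were 0.87, 2.02, 4.59 and 3.43. These figures show the structure and do not estimate bias. Extent: 2 tables × 4 visits = 8 printed odds ratios, but 2 distinct values (one per population) if fitted as listed.

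Cost of the interaction: 4 − 1 = 3 more parameters. An early visit may also have no events in the vehicle arm. The documents give no Week 2 rate. At assumed rates of 1%, 2%, 3% and 4%, the probability of no events among 100 is:

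- 0.99^100 = 36.6%
- 0.98^100 = 13.3%
- 0.97^100 = 4.8%
- 0.96^100 = 1.7%

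At the Week 8 planning rate it is 0.902^100 = 0.003%.

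A zero-event visit can bring down the whole fit as well as its own row. In 20 simulated datasets with no vehicle events at Week 2 and the interaction included, the fit failed in 18 with unstructured correlation, in 11 with exchangeable and in none with independence. In a separate set of 30, unstructured errored in 12. Exchangeable did not converge in 10 and gave an absurd Week 8 value in one more. Independence converged in all 30. Rates were assumed and the software was not SAS, so the failure frequencies are indicative only.

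**The case against.** On (a), one could say that a composite responder endpoint was meant. The shells rule that out, because they put the achievers in the denominator. It is fair to add that the Week 8 failure reveals itself: software returns no statistic, so no false P value can appear there. The grade counts also remain usable as description.

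On (b), the defence is stronger. This SAP's model lists are shorthand elsewhere. The ANCOVA lists in Sections 8.2.2 to 8.2.4 and 8.3, and footnote 1 of Table 14.2.3.7, omit treatment itself although treatment contrasts are required. The Cox description in Section 8.2.2 names only stratification factors yet reports a hazard ratio between arms. Read in that light, a row per visit is good evidence that visit-specific effects were intended. This stands, and it reduces (b) to a clarification. A reader might infer that the GEE simply fails to deliver a Week 8 estimate. That is true only of the literal term list, and the documents do not establish that the model would be fitted that way.

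A reader might also infer that the primary conclusion or type I error control is at risk. Section 8.1.1 confines the testing strategy for this endpoint to Week 8 in the ITT population. Robustness at Week 8 is covered by the nonimputed CMH and by the tipping-point analysis in Section 6.1.4.2. Neither depends on these tables.

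**Conclusion.** Part (a) is an error as written and follows from the definition of the subgroup: four Week 8 comparisons that cannot be computed and twelve that are not randomised comparisons. The subset sizes rest on assumed B-IGA rates and overlap, but the error does not.

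Part (b) is an under-specified model. Taken literally it yields one odds ratio repeated four times, and the layout suggests otherwise. The numerical effect on the Week 8 row is unknown and may be small, so no estimate is offered.

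Both analyses are supportive, and severity is low. The correction is worth making because it is nearly free and removes choices that should not be left to programming.

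**What to change.** **(a)** Remove the achiever item from the CMH subgroup lists in Sections 8.1.1 and 10. Delete the odds ratio, CI and P value rows from Tables 14.2.1.5.5, 14.2.1.6.5, 14.2.1.7.6 and 14.2.1.8.6, and label these tables descriptive, including their titles in Table 5. Nothing more is needed to correct the error.

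A composite analysis of S-IGA and B-IGA success, both at Week 8, is optional. If it is added:

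- A subject with one observed Week 8 failure should count as a nonresponder even when the other score is missing.
- The SAP must say which missing-data rule governs the rest. Section 6.1.4.1 says "For responder analyses, missing data will be treated as a nonresponse with the exception of S-IGA", whereas Section 8.2.1 analyses B-IGA as observed.
- It should not be called a multiple-imputation result unless B-IGA is imputed too. Section 6.1.4.1 imputes S-IGA and then says "Other missing data will not be imputed" (incomplete dates apart). The two scores are likely to be missing together: they share a visit schedule, and they head the list in Section 6.2 introduced by "The following assessments cannot be completed via telemedicine/remotely".

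**(b)** Add treatment-by-visit to the GEE in Section 8.1.1 and to footnote 3 of Table 14.2.1.9, which Table 14.2.1.10 shares. Name the Week 8 contrast as the sensitivity estimate. Add an independence working correlation with robust standard errors as the final fallback in footnote 3, or state that an early visit with no events in an arm is dropped from the model.

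**Cost.** Wording in two sections, four shells and their titles, one shared footnote and one model statement; no new data. The downside of (b) is three more parameters and possible instability at an early visit. The GEE still does not adjust for baseline B-IGA, so its Week 8 odds ratio need not equal the CMH odds ratio.
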